## 7.2. Clinical Laboratory Parameters

Descriptive statistics for laboratory values (in US conventional and SI units) and changes from baseline at each assessment time point will be presented for the following laboratory parameters collected in the study including but are not limited to the following:

- Hematology: hemoglobin, hematocrit, RBC count, MCV, MCH, MCHC, WBC count, neutrophils, lymphocytes, monocytes, eosinophils, basophils, and platelet counts
- Chemistry: alkaline phosphatase, ALT, AST, bicarbonate, total bilirubin, BUN, chloride, creatinine, potassium, total protein, and sodium.

Laboratory tests values are clinically significant (CS) if they meet either the low or high CS defined by the normal ranges at the site's local laboratory. The number and percentage of subjects with post-Baseline CS values will be tabulated by treatment group. The percentages are to be calculated relative to the number of subjects with available non-CS baseline values and at least one post-Baseline assessment. The numerator is the total number of subjects with at least one post-Baseline CS value. In addition, shift tables will be presented by treatment group and time point. The following three data listings will be presented by subject:

- A listing of lab values for all lab tests at all collected time points.
- A listing of subjects with post-Baseline CS values will be provided including the Baseline and post-Baseline values.
- A listing of all AEs for subjects with CS laboratory values will also be provided.

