#### **4.4.3 Clinical Laboratory Tests**

##### **4.4.3.1. Hematology Tests**

The hematology panel will be performed on blood obtained at Baseline, Week 8 Session 2 Light Session visit prior to the light session, and End of Study. The panel will consist of the following tests:

- Red blood cell count (RBC)
- Hematocrit
- Hemoglobin
- Mean corpuscular volume (MCV)
- Mean corpuscular hemoglobin (MCH)
- Mean corpuscular hemoglobin concentration (MCHC)
- Platelet count
- White blood cell count (WBC)
- Percent and absolute neutrophil count
- Percent and absolute lymphocyte count
- Percent and absolute monocyte count
- Percent and absolute eosinophil count
- Percent and absolute basophil count

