**Table 9: Ranges of Potentially Clinically Significant Lab Values**

Parameter	SI Unit	Lower Limit	Higher Limit
CHEMISTRY			
Alanine			
Aminotransferase (ALT)	U/L		≥3 * UNL
Alkaline Phosphatase	U/L		≥3 * UNL
Aspartate Aminotransferase (AST)	U/L		≥3 * UNL
Bicarbonate	mmol/L		≥3 * UNL
Creatinine	mg/dL		>1.5 * Day 1
Potassium	mmol/L	<0.75*LLN	>1.2 * UNL
Sodium	mmol/L	<0.9*LLN	>1.1 * UNL
Chloride	mmol/L		
Total Bilirubin	mg/dL		>1.5 * UNL
Total Protein	g/dL	<0.9*LLN	>1.1 * UNL
Urea (BUN)	mg/dL		>1.5 * Day 1
HEMATOLOGY			
Red blood cell count (RBC)	10  /µL		
Hematocrit	%		
Hemoglobin	g/dL		
Mean corpuscular volume (MCV)	fL		
Mean corpuscular hemoglobin (MCH)	pg		
Mean corpuscular hemoglobin concentration (MCHC)	g/dL		
Neutrophil Percentage	%		

Parameter	SI Unit	Lower Limit	Higher Limit
Neutrophil Count	$10^3/\mu\text{L}$	$\leq 1$	
Lymphocyte Percentage	%		
Lymphocyte Count	$10^3/\mu\text{L}$		
Monocyte Percentage	%		
Monocyte Count	$10^3/\mu\text{L}$		
Eosinophil Percentage	%		
Eosinophil Count	$10^3/\mu\text{L}$		
Basophil Percentage	%		
Basophil Count	$10^3/\mu\text{L}$		
Platelet Count	$10^3/\mu\text{L}$	$\leq 100$	$\geq 700$
White Blood Cell Count	$10^3/\mu\text{L}$	$\leq 2.5$	$\geq 15$

LLN: Lower limit of normal, value provided by the laboratory

ULN: Upper limit of normal, value provided by the laboratory

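### SAP 7.2 defines clinically significant laboratory values by the local normal range, while Table 9 sets much wider limits that Section 8.5 uses for a different purpose; the three need to be reconciled

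*SAP*

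**What the plan says.** SAP 7.2 gives the rule for a clinically significant (CS) laboratory value: "Laboratory tests values are clinically significant (CS) if they meet either the low or high CS defined by the normal ranges" of the local laboratory. It gives no multiplier, minimum change from baseline, repeat test or reference to Table 9. The denominator is set "relative to the number of subjects with available non-CS baseline values and at least one post-Baseline assessment". For the numerator: "The numerator is the total number of subjects with at least one post-Baseline CS value". Section 7.2 also provides descriptive statistics, changes from baseline, shift tables and three listings.

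Table 9 in SAP Appendix 1 is titled "Ranges of Potentially Clinically Significant Lab Values". Its limits include:
- ALT, AST and alkaline phosphatase at ≥3*UNL;
- potassium at <0.75*LLN or >1.2*UNL;
- total bilirubin at >1.5*UNL;
- creatinine and BUN at >1.5 times the Day 1 value;
- absolute limits for neutrophil, platelet and white cell counts.

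SAP 8.5 cites Tables 8 and 9, but for sorting results into low, normal and high groups. It does not mention CS.

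**The concern.** The table whose title announces clinically significant ranges is not used for the CS rule, and the rule that should separate inside from outside the normal range is sent to that table. The two pointers look interchanged.

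Read literally, an ALT of 1.01 times the upper limit is CS under 7.2, although Table 9 does not call it even potentially significant. An ALT of 2.9 times the upper limit would be grouped as normal under 8.5.

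Safety laboratory tests are the secondary endpoint of an uncontrolled study of about 6 patients, so no arm shows the background rate. If programmers follow 7.2 as written, ordinary variation will be tabulated and listed as clinically significant under treatment. If they follow Table 9, the counts will be far smaller. The plan does not settle which.

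**Working it through.** The plan states no false-flag rate, so there is none to reproduce.

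**Inputs from the documents**
- Post-baseline laboratory visits: 2. Blood is drawn "at Baseline, Week 8 Session 2 Light Session visit prior to the light session, and End of Study" (SAP 4.4.3.1; chemistry has the same schedule).
- Tests: 7.2 lists 13 hematology tests ("hemoglobin, hematocrit, RBC count, MCV, MCH, MCHC, WBC count, neutrophils, lymphocytes, monocytes, eosinophils, basophils, and platelet counts") and 11 chemistry tests ("alkaline phosphatase, ALT, AST, bicarbonate, total bilirubin, BUN, chloride, creatinine, potassium, total protein, and sodium"), 24 in all. Table 9 splits the five differentials into percent and count, giving 24 + 5 = 29 rows.
- Table 9 rows with a limit: 10 chemistry (all but chloride) and 3 hematology (neutrophil count, platelets, white cells), 13 in all. Blank rows: 29 − 13 = 16, including hemoglobin and chloride.
- Patients: about 6 (Protocol 5.1).

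**Assumptions not in the documents.** The normal range covers the central 95% of values. Values are normal with within-person correlation ρ. There is no drug effect.

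**Per-test noise under the plain reading of 7.2.** For a patient with personal level s, the chance that one value is in range is g(s) = Φ((1.96 − √ρ·s)/√(1−ρ)) − Φ((−1.96 − √ρ·s)/√(1−ρ)). The chance of at least one of two post-baseline values out of range, given an in-range baseline, is p = 1 − E[g³]/E[g].

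| ρ | p |
|---|---|
| 0 | 1 − 0.95² = 9.7% |
| 0.5 | 7.9% |
| 0.7 | 6.2% |
| 0.85 | 4.4% |

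**Expected flags in 6 patients, all in range at baseline.**
- Low end: 6 × 24 × 0.044 = 6.3.
- High end: 6 × 29 × 0.079 = 13.7.

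With 95% in range on each test these become 6.0 and 13.1. The expected count does not depend on correlation between tests. On any one test, a single flagged patient among 6 shows as 1/6 = 17%.

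**Share of patients with any flag.** This does depend on between-test correlation q. By simulation:
- 29 tests, ρ = 0.5, q = 0: 90%.
- 29 tests, ρ = 0.85, q = 0.6: 44%.
- 24 tests, ρ = 0.9, q = 0.6: 36%.

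**Role of the baseline restriction.** Without it, the per-test rate is 1 − E[g²]: 8.3% at ρ = 0.7 (against 6.2% with it) and 7.5% at 0.85 (against 4.4%). The restriction lowers the flag rate.

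**Numerator against denominator.** The denominator takes "The percentages are to be calculated relative to the number of subjects with available non-CS baseline values", but the numerator carries no such limit. If 1 of 6 patients is CS at baseline and stays so, the table reads 1/5 = 20% with no new event.

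**Noise under Table 9.** Typical normal ranges and a within-person CV for BUN have to be assumed. Over two visits, the limited tests without BUN flag about 3% of patients. With a BUN CV of 12%, 15% or 20%, the totals are about 5%, 8% and 17%.

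**The case against.** The best defence is that 7.2 already means Table 9. Several Table 9 limits are multiples of the laboratory's own LLN or UNL, 8.5 speaks of scaled limits, and a plain out-of-range rule would hardly need separate low and high CS values. This is a possible reading, and on it creatinine and BUN do carry a minimum change. But 7.2 names the normal ranges and not the table, while 8.5 ties the table to low/normal/high grouping. The defence therefore shows that two readings exist; it does not remove the conflict. SAP Table 7 shows the contrast: a vital sign is CS only with both an extreme value and a minimum change.

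Four stronger inferences are tempting and are not supported:
- **That noise would make half to nine-tenths of patients significant on some test.** The top of that range needs 29 independent tests, which is implausible for hemoglobin with hematocrit, or for percent with absolute counts. Strong correlation brings the figure to about one third. Section 7.2 also does not say that an any-test percentage will be tabulated.
- **That selecting patients in range at baseline causes the false flags.** The restriction lowers the rate, it is written for the denominator only, and the entry criteria contain no laboratory limit.
- **That signal could not be told from noise.** Every value is listed for about 6 patients, with baseline and post-baseline values for those flagged. Protocol 10.2 also highlights results beyond 2 SD. A careful reader can see how far out a value lies.
- **That Table 9 brings noise close to zero.** This holds for potassium under an assumed range (limits more than 4 SD from the mean), but not across the table.

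**Conclusion.** The conflict between 7.2, 8.5 and Table 9 is real and should be resolved before the tables are programmed. Under the plain reading of 7.2, chance alone gives a CS flag in about 4% to 8% of in-range patients per test, or roughly 6 to 14 flags in the study. These figures rest on central-95% ranges, normal values and within-person correlation of 0.5 to 0.85. The any-test share, about one third to nine-tenths, is too dependent on assumed correlations to serve as a headline.

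The consequence is mislabelling in the CS tables, the CS listing and the listing of adverse events for CS subjects. No test or decision rule depends on these counts, and the full listings limit the harm.

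**What to change.** Change SAP wording in two sections:
1. In 7.2, define CS by the existing Table 9 limits and cite the table.
2. In 8.5, base low/normal/high grouping, and hence the shift tables, on the laboratory's plain normal range.
3. For the 16 rows with no Table 9 limit, report values outside the local range as out of range in listings and shift tables, not as CS.
4. In 7.2, restrict the numerator to subjects in the denominator, that is, those with a non-CS baseline and a post-baseline assessment.

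No data collection changes. The cost is that tests without a Table 9 limit, hemoglobin among them, leave the CS percentage unless a limit is added. Some noise also remains: roughly 3% to 17% of patients on the assumptions above, mainly from BUN.

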#### **5.3.2 Baseline**

After enrollment but prior to application of HyBryte the following assessments will be performed:

Interval medical history from screening obtained

Complete Physical Examination

Vitals taken (heart rate, respiratory rate, and sitting blood pressure)

Hematology panel drawn

Clinical chemistry panel drawn

Pregnancy test results reviewed

Three lesions that are representative of the patient's disease and are discrete with defined borders, will be chosen as the index lesions, and classified as patch or plaque lesions

Charting of all CTCL lesions on the "Body Lesion Diagram" form ([Appendix II](#)) locating and numbering each of the index lesion

Each of the index lesions will have a CAIIS score assessed and recorded

The mSWAT score will be assessed and recorded

5 mL of blood obtained and processed for serum hypericin levels

12-lead ECG obtained including QT interval measurements

The patient will complete the Skindex-29 ([Appendix III](#)) and VASitch forms and the data transcribed into the eCRF

A jar of ointment will be issued and the weight of the jar prior to dispensation will be recorded

Only after all of the above have been completed, patients will be instructed on proper drug application and demonstrate proficiency in drug application and all accessible lesions will be treated with study drug

The weight of the jar after drug application will be recorded

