#### **5.4 Premature Discontinuation**

Patients have the right to withdraw from this trial at any time (as described in the informed consent document) without prejudice to further care. An investigator may withdraw a patient from the study at any time for any of the following reasons:

- The patient withdraws his/her consent or refuses follow-up evaluations.
- The patient is lost to follow-up and will not attend further study visits.
- The investigator determines that further participation would be detrimental to the patient's health or well-being.
- The patient fails to comply with the study requirements so as to cause harm to self or seriously interfere with the validity of the study results.
- The female patient becomes pregnant during the treatment period. In this case, treatment should be halted and the patient followed until the end of the pregnancy. If a child is born, the infant should be followed through at least 6 months of age.
  - At the discretion of the site investigator if he/she feels that it is in the best medical interest of the patient.

Patients withdrawn from the study will have as many of the trial assessments completed as the patient permits including blood tests and lesion evaluations.

Patients withdrawn from the study may be replaced up to a total of 8 subjects provided that both the PI and the Soligenix Medical Monitor agree that the reasons for withdrawal do not suggest a change in the risk assessment of the HyBryte therapy.

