### 5.4. Additional Data Handling Rules and Presentation Specifications

The following general guidelines will apply to all statistical analyses and data presentations:

Baseline is defined as the last available value obtained prior to the first dose of study drug, unless otherwise specified in this SAP.

By default, US conventional units will be used for laboratory value presentations. A set of lab summary tables in International Standard Units (SIU) will also be provided based on tables, listings and figures.

Age is calculated as of date that the informed consent form was signed - age = floor ((date of Informed Consent – birth date+1)/365.25)

All percentages will be rounded to one decimal place and lined up by the decimal place. The percentage will be suppressed when the count is zero.

Any p-values will be rounded to three decimal places and will be presented as ‘<0.001’ if they are less than 0.001 after rounding.

For continuous variables that are recorded as “< X” or “> X”, the value of “X” will be used in the calculation of summary statistics. The original values will be used for the listings.

Decimal points will be presented as follows: N will be presented without decimal, minimum and maximum in same precision as in the database, mean and median in one more decimal than minimum and maximum, and SD in one more decimal than mean and median.

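### The laboratory CS percentage in SAP 7.2 counts subjects in its numerator whom it leaves out of its denominator

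*SAP*

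**What the plan says.** SAP 7.2 defines one percentage in two consecutive sentences. The denominator: "The percentages are to be calculated relative to the number of subjects with available non-CS baseline values and at least one post-Baseline assessment". The numerator: "The numerator is the total number of subjects with at least one post-Baseline CS value". The first has a condition on baseline status and the second has none. No other section of the SAP or protocol supplies one.

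The same section plans other displays that show baseline status: "In addition, shift tables will be presented by treatment group and time point", and "A listing of subjects with post-Baseline CS values will be provided including the Baseline and post-Baseline values". It also plans a listing of all laboratory values. Protocol 10.2 adds per-patient listings.

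On the meaning of CS, SAP 7.2 refers to the normal ranges of the site's local laboratory and does not cite Table 9. SAP 8.5 sorts results into low, normal and high by scaled laboratory limits and points to Tables 8 and 9. Table 8 contains only numeric codes for results reported as character strings. Table 9 is headed as potentially clinically significant ranges. It mixes multiples of laboratory limits, absolute cut-offs and multiples of the Day 1 value.

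**The concern.** A percentage whose numerator is not a subset of its denominator cannot be interpreted. Here a subject who was already CS at baseline, and is CS again later, raises the numerator while being removed from the denominator. The mismatch can only push the figure upward. In a single-arm study with no comparator, a pre-existing abnormality can then read as one that appeared on treatment.

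Routine safety laboratory results are the secondary endpoint in SAP 4.2, and the study plans about 6 subjects, so a single subject moves the figure visibly.

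The unclear CS definition bears on this directly, because it decides on which tests a subject can be CS at baseline at all.

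**Working it through.** **Can the case arise?** The entry criteria (Protocol 5.2.1 and 5.2.2) set no laboratory limit, and the screening visit (5.3.1) includes no hematology or chemistry panel. The panels are first drawn at the Baseline visit: "After enrollment but prior to application of HyBryte the following assessments will be performed". Nothing therefore screens out a subject with a CS value at baseline.

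A subject with no usable baseline value and a later CS value would also be counted only above the line. This should be rare. Both panels precede the first application ("Only after all of the above have been completed, patients will be instructed on proper drug application"), so it would take a lost or unusable sample. If that happened, there would be no screening panel to fall back on under the SAP 5.4 rule: "Baseline is defined as the last available value obtained prior to the first dose of study drug".

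**Inputs.** The planned size is about 6 (Protocol 5.1). The maximum with replacement is 8 (Protocol 5.4): "Patients withdrawn from the study may be replaced up to a total of 8 subjects". The documents state no CS rate, so there is no figure of the plan's own to reproduce, and the case counts below are illustrative assumptions. SAP 7.2 does not say whether the percentage is per test or pooled over tests. I work per test; the mismatch arises either way.

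**Formulas.** For one test, let N be the subjects with a baseline value and a post-baseline assessment, B those CS at baseline, r those of the B who are CS again later, and e the subjects newly CS.

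- As written: (r + e) / (N − B)
- Numerator restricted to the denominator set: e / (N − B)
- Excess: r / (N − B)

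| N | B | r | e | As written | Restricted |
|---|---|---|---|---|---|
| 6 | 1 | 1 | 0 | 1/5 = 20.0% | 0/5 = 0% |
| 6 | 2 | 1 | 0 | 1/4 = 25.0% | 0/4 = 0% |
| 6 | 2 | 2 | 1 | 3/4 = 75.0% | 1/4 = 25.0% |
| 6 | 3 | 3 | 1 | 4/3 = 133.3% | 1/3 = 33.3% |
| 6 | 1 | 0 | 1 | 1/5 = 20.0% | 1/5 = 20.0% |
| 8 | 1 | 1 | 0 | 1/7 = 14.3% | 0/7 = 0% |
| 8 | 2 | 1 | 0 | 1/6 = 16.7% | 0/6 = 0% |
| 8 | 2 | 2 | 1 | 3/6 = 50.0% | 1/6 = 16.7% |
| 8 | 4 | 4 | 1 | 5/4 = 125.0% | 1/4 = 25.0% |

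The fifth row shows the condition for no error: r = 0, for example when the baseline-CS subject normalises. The as-written figure passes 100% whenever r + e > N − B; the restricted one cannot.

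**Reach under each CS definition.** Table 9 lists 11 chemistry and 18 hematology tests, 29 in all. Under local normal ranges, any test with a local range can be affected, so up to 29. Under Table 9 as it appears in the text available to me, chloride and 15 hematology tests have no limit (1 + 15 = 16), so they can never be CS. Creatinine and BUN are judged against 1.5 times Day 1, so they cannot be CS at baseline if Day 1 is the baseline (assumption). That leaves 29 − 16 − 2 = 11 tests: ALT, AST, alkaline phosphatase, bicarbonate, potassium, sodium, total bilirubin, total protein, neutrophil count, platelets and white cells.

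**The case against.** The strongest reply is that this is a drafting slip. The first sentence sets the population and the second says what counts as an event, so an ordinary reader would draw events from the population just defined. That is probably the intent. But the numerator sentence refers to the total number of subjects, and the SAP's introduction requires departures from the SAP to be described and justified in the study report. A programmer must either produce the mismatched figure or deviate.

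A second reply is that the shift tables and listings separate new from carried-over abnormalities, so with about 6 subjects the right figure can be recovered. This is true and limits the harm, but the tabulated percentage stays wrong.

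Third, the larger examples are hypothetical: 133% needs three of six subjects persistently CS on the same test plus one new case. The rows for 8 are also favourable. The total reaches 8 only by replacing withdrawn patients, the scheduled post-baseline panels fall only at Week 8 and End of Study, and a patient who withdraws before Week 8 contributes only if a blood test is taken at withdrawal. Both points stand; the one-subject case is the fair minimum illustration.

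Fourth, the CS definitions may serve different outputs: CS in 7.2, low/normal/high grouping in 8.5, potentially CS in Table 9. That is possible, so this part is a request to reconcile and not a proven contradiction. The counts of blank Table 9 rows also depend on the table having been extracted correctly from the PDF.

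**Conclusion.** As written, the rule gives a wrong percentage for any test on which at least one subject is CS at baseline and again later. The smallest such error, with one baseline-CS subject, is 20 percentage points at 6 assessed subjects and 14.3 points at 8. How often it will occur cannot be estimated from the documents.

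The consequence is modest. The study is descriptive, no decision rule uses this percentage, and no primary endpoint is touched. The correction is still worth making, because the error always overstates and costs almost nothing to remove. This conclusion rests on the numerator alone and does not depend on how the CS definition is resolved.

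**What to change.** In SAP 7.2, restrict the numerator to subjects in the denominator: those with a non-CS baseline value on the test and at least one CS value on that test after baseline. Show subjects who were already CS at baseline, or who have no baseline value, on a separate line.

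In the same section, state whether CS means the local laboratory's normal range or the Table 9 limits, and reconcile SAP 7.2, 8.5 and Table 9 accordingly. If Table 9 applies, say how tests without a limit are handled (16 as extracted).

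The cost is one clause, one extra table line, and a sentence or two on the definition. No new data are needed.
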